3.2.3 Efficacy - Exploratory Endpoints

- Mean change (absolute and percent) in IGA from Baseline to Week 4
- Mean change (absolute and percent) in EASI from Baseline to Week 4

STATISTICAL ANALYSIS PLAN

Version 3.0 12-Jan-22

- Proportion of subjects with IGA of Clear or Almost Clear and ≥2 point improvement from Baseline to Week 4
- Proportion of subjects with IGA of Clear or Almost Clear at Week 4
- Proportion of subjects with any improvement in IGA from Baseline to Week 4
- Proportion of subjects with ≥50% Improvement in EASI (EASI-50) from baseline to Week 4
- Proportion of subjects with ≥75% Improvement in EASI (EASI-75) from baseline to Week 4
- Proportion of subjects with ≥90% Improvement in EASI (EASI-90) from baseline to Week 4.

The endpoints will be reported for all visits. Absolute change will be considered the primary endpoint with percent change as supportive. Any improvement in IGA is defined as ≥ 1 point improvement from Baseline.

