4.1.1 Inclusion-Exclusion Criteria and General Study Population

4.1.1.1 Inclusion Criteria

Deviations from inclusion criteria are not allowed because they can potentially jeopardize the scientific integrity of the study, regulatory acceptability, or participant safety. Therefore, adherence to the criteria as specified in the protocol is essential.

Participants eligible for enrollment in the study must meet all the following criteria:

- 1. Male and female subjects 18 to 65 years of age.
- 2. Pruritus of at least 4 weeks duration prior to the initial Screening visit and during the 2 week washout period.
 - a. Subjects using stable doses of oral H1 antihistamines at the initial Screening visit must be willing to continue these at the same doses and frequencies throughout the study inclusive of the follow-up period.
- 3. Worst Itch Numeric Rating Scale (WI-NRS) score ≥ 7 in the 24-hour period prior to the initial Screening as well as Baseline visits.
- 4. Average weekly WI-NRS score ≥6 for each week of the washout period, as recorded in the eDiary.
- 5. A history of atopic dermatitis for greater than 12 months consistent with a diagnosis of atopic dermatitis, as defined by the 2014 American Academy of Dermatology (AAD) Guidelines of Care for the Management of Atopic Dermatitis².
 - a. Subjects using bland emollients at the initial Screening visit will be allowed to continue to use their emollient of choice at a similar dose and frequency throughout the study, if used.

STATISTICAL ANALYSIS PLAN

Version 3.0 12-Jan-22

- b. Subjects using low- to mid-potency topical corticosteroids at the initial Screening visit will be allowed to use their topical corticosteroid of choice at the same dose and frequency no more than 7 days per month throughout the study as rescue medication.
- 6. A minimum of 10% and not more than 40% of the subjects' BSA affected by atopic dermatitis (*affected* is defined by physical examination findings: erythema, edema, scaling, lichenification, excoriation, with the excoriation serving as the physical examination correlate of pruritus) at Screening and Baseline.
 - a. Subjects' BSA can include face and body OR body alone BUT NOT face alone.
- 7. An Investigator Global Assessment (IGA) score of 2-3 at Screening and Baseline.
- 8. Willing and able to complete once-daily eDiary entries within a consistent timeframe for the duration of the study and have ≥80% eDiary compliance rate during the washout period.

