7.4.3 Analysis of IGA, EASI, POEM, 5-D Pruritus Scale

The endpoints IGA, EASI, POEM, 5-D Pruritus Scale will be summarized using descriptive statistics and analyzed using a logistic regression model at each respective timepoints. Mean change from Baseline to Week 2, Week 4, and Week 8 in IGA, EASI, POEM, and 5-D Pruritus Scale, as well as IGA and EASI responders, will be analyzed for mITT and PP as described in section 7.4.

Responder status is determined by reaching a certain level of improvement as defined below. Responder status varies by outcome measure, endpoint, and visit. That is, a subject can be considered a responder at one visit, but not the next for a specific measure. Similarly, a subject can be considered a responder for one measure but not another at the same visit. Responder criteria for categorical measures are as follows:

- Proportion of subjects with an IGA 0 (clear) or 1 (almost clear) and \geq 2-point improvement from Baseline will be reported for Week 2, Week 4, and Week 8.
- Proportion of subjects with IGA 0 (clear) or 1 (almost clear) will be reported for Week 2, Week 4, and Week 8.
- Proportion of subjects with any improvement in IGA from Baseline (defined as ≥1 point change from Baseline) will be reported for Week 2, Week 4, and Week 8.
- Proportion of subjects with at least 50%, 75%, and 90% improvement in EASI (EASI-50, EASI-75, and EASI-90, respectively) from Baseline will be reported for Week 2, Week 4, and Week 8.

Each of these outcomes will be compared between treatment groups using a logistic regression model by week. Generalized estimating equations to account for repeated measures and within-subject variability may also be applied.

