- Repeat for 14.2.2.15.6 Proportion of Subjects with \geq 90% Improvement in EASI (EASI-90) from Baseline to Weeks 2, 4, and 8 Non-Responder Imputation (NRI) Analysis for PP Population
 - \circ Footnotes [1,3] will be same as in 14.2.2.13.6.
 - Footnote [2] will be same as in 14.2.2.13.1, except changing "50%" to "90%"
- Repeat for 14.2.2.16.1 Proportion of Subjects with IGA of Clear or Almost Clear and ≥2 Point Improvement from Baseline to Weeks 2, 4, and 8 Primary Analysis for mITT Population
 - Footnotes [1,3] will be same as in 14.2.2.13.1.
 - Footnote [2]: Treatment response is improvement by ≥ 2 Points in IGA score to Clear or Almost Clear.

- Repeat for 14.2.2.16.2 Proportion of Subjects with IGA of Clear or Almost Clear and ≥2 Point Improvement from Baseline to Weeks 2, 4, and 8 Sub-Analysis for mITT Population
 - Footnotes [1,3] will be same as in 14.2.2.13.2.
 - Footnote [2] will be same as in 14.2.2.16.1.
- Repeat for 14.2.2.16.3 Proportion of Subjects with IGA of Clear or Almost Clear and ≥2 Point Improvement from Baseline to Weeks 2, 4, and 8 Non-Responder Imputation (NRI) Analysis for mITT Population
 - \circ Footnotes [1,3] will be same as in 14.2.2.13.3.
 - Footnote [2] will be same as in 14.2.2.16.1.
- Repeat for 14.2.2.16.4 Proportion of Subjects with IGA of Clear or Almost Clear and ≥2 Point Improvement from Baseline to Weeks 2, 4, and 8 Primary Analysis for PP Population
 - Footnotes [1,3] will be same as in 14.2.2.13.4.
 - Footnote [2] will be same as in 14.2.2.16.1.
- Repeat for 14.2.2.16.5 Proportion of Subjects with IGA of Clear or Almost Clear and ≥2 Point Improvement from Baseline to Weeks 2, 4, and 8 Sub-Analysis for PP Population
 - \circ Footnotes [1,3] will be same as in 14.2.2.13.5.
 - Footnote [2] will be same as in 14.2.2.16.1.
- Repeat for 14.2.2.16.6 Proportion of Subjects with IGA of Clear or Almost Clear and ≥2 Point Improvement from Baseline to Weeks 2, 4, and 8 Non-Responder Imputation (NRI) Analysis for PP Population
 - \circ Footnotes [1,3] will be same as in 14.2.2.13.6.
 - Footnote [2] will be same as in 14.2.2.16.1.
- Repeat for 14.2.2.17.1 Proportion of Subjects with IGA of Clear or Almost Clear at Weeks 2, 4, and 8 Primary Analysis for mITT Population
 - \circ Footnotes [1,3] will be same as in 14.2.2.13.1.
 - Footnote [2]: Treatment response is improvement by ≥ 2 Points in IGA score.

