- Repeat for 14.2.2.17.2 Proportion of Subjects with IGA of Clear or Almost Clear at Weeks 2, 4, and 8 Sub-Analysis for mITT Population
 - \circ Footnotes [1,3] will be same as in 14.2.2.13.2.
 - Footnote [2] will be same as in 14.2.2.17.1.
- Repeat for 14.2.2.17.3 Proportion of Subjects with IGA of Clear or Almost Clear at Weeks 2, 4, and 8 Non-Responder Imputation (NRI) Analysis for mITT Population
 - Footnotes [1,3] will be same as in 14.2.2.13.3.
 - Footnote [2] will be same as in 14.2.2.17.1.
- Repeat for 14.2.2.17.4 Proportion of Subjects with IGA of Clear or Almost Clear at Weeks 2, 4, and 8 Primary Analysis for PP Population
 - \circ Footnotes [1,3] will be same as in 14.2.2.13.4.
 - Footnote [2] will be same as in 14.2.2.17.1.
- Repeat for 14.2.2.17.5 Proportion of Subjects with IGA of Clear or Almost Clear at Weeks 2, 4, and 8 Sub-Analysis for PP Population
 - Footnotes [1,3] will be same as in 14.2.2.13.5.
 - Footnote [2] will be same as in 14.2.2.17.1.
- Repeat for 14.2.2.17.6 Proportion of Subjects with IGA of Clear or Almost Clear at Weeks 2, 4, and 8 Non-Responder Imputation (NRI) Analysis for PP Population
 - \circ Footnotes [1,3] will be same as in 14.2.2.13.6.
 - Footnote [2] will be same as in 14.2.2.17.1.
- Repeat for 14.2.2.18.1 Proportion of Subjects with Any IGA Improvement from Baseline to Weeks 2, 4, and 8 Primary Analysis for mITT Population
 - Footnotes [1,3] will be same as in 14.2.2.13.1.
 - \circ Footnote [2]: Treatment response is any improvement in IGA score. Any improvement is defined as ≥ 1 point improvement from Baseline.
 - Repeat for 14.2.2.18.2 Proportion of Subjects with Any IGA Improvement from Baseline to Weeks 2, 4, and 8 Sub-Analysis for mITT Population
 - \circ Footnotes [1,3] will be same as in 14.2.2.13.2.
 - Footnote [2] will be same as in 14.2.2.18.1.

- Repeat for 14.2.2.18.3 Proportion of Subjects with Any IGA Improvement from Baseline to Weeks 2, 4, and 8 Non-Responder Imputation (NRI) Analysis for mITT Population
 - Footnotes [1,3] will be same as in 14.2.2.13.3.
 - Footnote [2] will be same as in 14.2.2.18.1.
- Repeat for 14.2.2.18.4 Proportion of Subjects with Any IGA Improvement from Baseline to Weeks 2, 4, and 8 Primary Analysis for PP Population
 - \circ Footnotes [1,3] will be same as in 14.2.2.13.4.
 - Footnote [2] will be same as in 14.2.2.18.1.
- Repeat for 14.2.2.18.5 Proportion of Subjects with Any IGA Improvement from Baseline to Weeks 2, 4, and 8 Sub-Analysis for PP Population

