Listing 16.2.6.5 IGA (Randomized Subjects)

| Subject ID | Treatment | Study Population | Visit | Date of Rating | Rating [1] | Clear or Almost Clear | Any Improvement [2] | ≥2-Point Improvement to Clear or Almost Clear |
|------------|--|--------------------------------|---|----------------|---|-----------------------|---------------------|---|
| XXXXXX | N/A, B244 O.D. 5.0, B244 O.D. 20.0, Vehicle | N/A, Safety, mITT, PP | Screening, Baseline, Week 2, Week 4, Week 8 | DDMMMYYYY | Clear, Almost Clear, Mild, Moderate, Severe | Yes, No | Yes, No | Yes, No |

[1] Numeric item conversion: Clear=0; Almost Clear=1; Mild=2; Moderate=3; Severe=4.

[2] Any improvement is defined as \geq 1 point improvement from Baseline. Source: SDTM.XXXX or ADaM.XXXX

PROGRAM NAME: XXXXXXXXX

Listing 16.2.6.6 EASI Items and Score (Randomized Subjects)

| Subject ID | Tractmont | Study Bopulation | Visit | Data of Pating | Pody Area | EASI Itom | Dating [1] | Improvement |
|------------|-----------------|---------------------|------------|----------------|--------------------|---------------------|------------|--------------------|
| Subject ID | Treatment | Fopulation | VISIL | | Body Alea | EASI Itelli | | mprovement |
| XXXXXX | N/A, | N/A, | Screening, | DDMMMYYYY | Head/Neck, | Erythema | None, | Null if $< 50\%$, |
| | B244 O.D. 5.0, | Safety, | Baseline, | | Trunk, | Edema/Papulation | Mild, | ≥50%, |
| | B244 O.D. 20.0, | mITT, | Week 2, | | Upper Extremities, | Excoriation | Moderate, | ≥75% |
| | Vehicle | PP | Week 4, | | Lower Extremities, | Lichenification, | Severe, | ≥90% |
| | | | Week 8 | | | Area Score (%) [2], | xx-xx%, | |
| | | | | | Total | Total Score | XXX | |

[1] Numeric item conversion: None=0; Mild=1; Moderate=2; Severe=3.

[2] Numeric area score conversion: 1-9%=0; 10-29%=2; 30-49%=3; 50-69%=4; 70-89%=5; 90-100%=6.

Source: SDTM.XXXX or ADaM.XXXX

PROGRAM NAME: XXXXXXXXXX

DATE: HH:MM/DDMMMYYYY

Programming Notes:

• Body Area=Total corresponds to EASI Item=Total Score.

Listing 16.2.7.1 Adverse Events (Safety Population)

| Subject ID | Treatment | System Organ Class/ Preferred Term [1] | AE # | Start Date | End Date/Ongoing | Serious | SAE Criteria | Treatment Emergent | | |
|----------------------------------|---|---|------|------------|-----------------------|---------|--------------|-----------------------|--|--|

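### The shell footnote for the exploratory IGA clear-or-almost-clear tables defines response as a 2-point fall, contradicting the table title and SAP sections 3.2.3 and 7.4.3

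*SAP*

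**What the plan says.** The SAP body treats two IGA responder endpoints as distinct. One requires IGA 0 or 1 together with a fall of at least 2 points. The other requires only IGA 0 or 1. Section 3.2.3 lists the second as "Proportion of subjects with IGA of Clear or Almost Clear at Week 4", and section 7.4.3 gives the criterion as "Proportion of subjects with IGA 0 (clear) or 1 (almost clear) will be reported for Week 2, Week 4, and Week 8". The efficacy analyses table in section 7.4 also names them separately.

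The shells in Appendix A, section 1.1.2, keep both endpoints:

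- **Tables 14.2.2.16.1 to 16.6** cover the first. Footnote 2 reads "Treatment response is improvement by ≥ 2 Points in IGA score to Clear or Almost Clear".
- **Tables 14.2.2.17.1 to 17.6** cover the second. The programming note names the first of them "Proportion of Subjects with IGA of Clear or Almost Clear at Weeks 2, 4, and 8 Primary Analysis for mITT Population", but its footnote 2 reads "Treatment response is improvement by ≥ 2 Points in IGA score". For each of 17.2 to 17.6 the instruction is "Footnote [2] will be same as in 14.2.2.17.1".

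Eligibility is "An Investigator Global Assessment (IGA) score of 2-3 at Screening and Baseline" (SAP 4.1.1.1). Listing 16.2.6.5 codes the scale from 0 for clear to 4 for severe.

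**The concern.** Footnote 2 is where these responder shells state the operational response rule. It gives at least 4 points for WI-NRS in 14.2.2.5.1, at least 50% for EASI in 14.2.2.13.1, and at least 1 point for IGA in 14.2.2.18.1. A programmer working from the 17.x shell would therefore code a change criterion for an endpoint that has none.

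Either way the output goes wrong. If the footnote is followed, six tables report a different endpoint from the one in their title. If section 7.4.3 is followed, the numbers are right but the printed footnote misdefines them. The baseline-IGA-2 stratum bears the whole effect: for those subjects the footnote turns clear or almost clear into complete clearance. That stratum is one of only two eligible baseline levels, and section 7.4 plans descriptive statistics by it.

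**Working it through.** The plan states no figure to reproduce here. The check is an enumeration.

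**Inputs.** Baseline IGA b is 2 or 3 (SAP 4.1.1.1). Visit IGA v is 0 to 4 (Listing 16.2.6.5).

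**Rules.**

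- A, footnote 2 of 14.2.2.16.1: v ≤ 1 and b − v ≥ 2
- B, footnote 2 of 14.2.2.17.1: b − v ≥ 2
- C, title of 14.2.2.17.1 and section 7.4.3: v ≤ 1

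**Result for eligible baselines.** Only pairs with v below b can meet any of the rules:

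| Baseline → visit | Fall | A | B | C |
|---|---|---|---|---|
| 2 → 1 | 1 | no | no | yes |
| 2 → 0 | 2 | yes | yes | yes |
| 3 → 2 | 1 | no | no | no |
| 3 → 1 | 2 | yes | yes | yes |
| 3 → 0 | 3 | yes | yes | yes |

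A and B give the same set, {2→0, 3→0, 3→1}. C adds 2→1. Compared with C, the footnote drops exactly one transition and adds none.

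**Do the tables match in other respects?** Yes. Footnotes 1 and 3 of 16.1 to 16.6 and of 17.1 to 17.6 both refer, table by table, to 14.2.2.13.1 to 13.6. The logistic model, the denominators and the handling of rescue use and non-responder imputation are therefore the same. For eligible subjects, 17.1 to 17.6 under rule B would repeat 16.1 to 16.6 number for number.

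**Ineligible baselines.** If a subject with baseline IGA 4 were enrolled as a deviation, B would also count 4→2, which meets neither A nor C. Only then do A and B differ. A subject with baseline IGA 1 would leave A and B equal, but 1→0 and 1→1 would also be dropped relative to C.

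**Size.** At a given visit and in a given arm, the proportion under B falls short of the proportion under C by p × q. Here p is the share of analysed subjects with baseline IGA 2, and q is the fraction of those with IGA exactly 1 at the visit. The documents give neither quantity, so the shortfall can lie anywhere from 0 to p. The direction of any effect on the odds ratios cannot be stated.

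**Where 2→1 is still counted or shown.**

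- Shift Tables 14.2.1.7.1 and 14.2.1.7.2 cross baseline with visit IGA at Weeks 2, 4 and 8.
- Tables 14.2.2.18.x count any fall of at least 1 point as response.
- Listing 16.2.6.5 has separate columns for the two endpoints.
- Figures 14.2.3.5 and 14.2.3.6 are titled for IGA 0 or 1.

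**The case against.** The best defence is that this is a drafting slip, not a rule. The title of 14.2.2.17.1, sections 3.2.3, 7.4 and 7.4.3, Listing 16.2.6.5 and two figures all state the endpoint correctly. The footnote looks carried over from the 16.1 footnote just above it. Section 6.3 says the shells convey expected layout and titles. A careful programmer would notice the clash and ask. The endpoint is also exploratory, was added by the SAP (section 7.7) and has no multiplicity control, and section 7.4 says such p-values are to be read as exploratory.

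Most of this stands as a limit on the consequences. It does not remove the error. Section 6.3 exempts changes of format and the like from documentation, but not real differences in analysis method or data handling, and a response definition belongs to the latter. Nothing in the SAP says that the title or body overrides a footnote.

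A reader might infer more than the documents support:

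- **That the clear-or-almost-clear endpoint would never be reported.** The listing and the two figures still plan it as IGA 0 or 1.
- **That all 2→1 changes would disappear from the outputs.** The shift tables and 14.2.2.18.x retain them; the loss is confined to the 17.x proportions and odds ratios.
- **That the sponsor chose a stricter definition.** The body text points the other way, so this is an internal inconsistency.
- **That addendum Table 14.2.2.17.7 carries the same error.** Only its title is available, and that title is correct; its footnotes are not in the text available for this review.

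**Conclusion.** The point holds in this limited form. Footnote 2 of Table 14.2.2.17.1, inherited by five further tables, contradicts the endpoint those tables are meant to report. For eligible subjects the footnote yields the 14.2.2.16.x response set and misclassifies every 2→1 subject in the 17.x proportions and odds ratios. Exact duplication assumes baseline IGA 2 or 3 throughout; a baseline-4 deviation moving to 2 would break it. The numerical effect cannot be given without the baseline IGA 2 share and the 2→1 rate. The harm to the estimates also depends on the footnote, not section 7.4.3, having been programmed. No primary or secondary endpoint is touched. The correction is worth making because the cost is trivial and six tables would otherwise be wrong or mislabelled.

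**What to change.** Replace footnote 2 of Table 14.2.2.17.1 with: *Treatment response is IGA of 0 (clear) or 1 (almost clear) at the visit.* Tables 14.2.2.17.2 to 17.6 then inherit the correct rule without further edits, and their response set becomes {2→0, 2→1, 3→0, 3→1}, distinct from 16.x.

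Confirm that Table 14.2.2.17.7 in the addendum (LOCF, ITT) uses the same definition. If the 17.x tables have already been run, check which rule the program applied and rerun them if it was the 2-point rule. The document change is one footnote, and no new data or model is needed.

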1.1.3 Safety

| Display Number | Title | Population | Unique/Repeat |
|----------------|--|------------|---------------|
| 14.3.1 | Overall Summary of Treatment | Safety | Unique |
| | Emergent Adverse Events | | |
| 14.3.1.1 | Summary of Treatment Emergent | Safety | Unique |
| | Adverse Events by System Organ Class | | |
| | and Preferred Term | | |
| 14.3.1.2 | Summary of Treatment Emergent | Safety | Repeat |
| | Adverse Events by System Organ | | |
| | Class, Preferred Term and Severity | | |
| 14.3.1.3 | Summary of Treatment Emergent | Safety | Repeat |
| | Adverse Events by System Organ | | |
| | Class, Preferred Term and Relationship | | |
| | to Study Drug | | |
| 14.3.1.4 | Summary of Severe (Grade 3) | Safety | Repeat |
| | Treatment Emergent Adverse Events | | |
| | by System Organ Class, Preferred | | |
| | Term and Relationship to Study Drug | | |
| 14.3.1.5 | Summary of Treatment Emergent | Safety | Repeat |
| | Adverse Events Leading to | | |
| | Discontinuation from Study by System | | |
| | Organ Class, Preferred Term | | |
| 14.3.1.6 | Summary of Treatment Emergent | Safety | Repeat |
| | Adverse Events with $\geq 2\%$ Frequency | | |
| | by System Organ Class, Preferred | | |
| | Term | | |
| 14.3.2.1 | Summary of Treatment Emergent | Safety | Repeat |
| | Serious Adverse Events by System | | |
| | Organ Class and Preferred Term | | |
| 14.3.2.2 | Summary of Treatment Emergent | Safety | Repeat |
| | Serious Adverse Events by System | | |

| | Organ Class, Preferred Term and | | |
|------------|-------------------------------------|--------|--------|
| | Relationship to Study Drug | | |
| 14.3.2.3 | Summary of Deaths | Safety | Unique |
| 14.3.4.1.1 | Summary of Values and Change from | Safety | Unique |
| | Baseline for Hematology Parameters | | |
| 14.3.4.1.2 | Shift from Baseline for Hematology | Safety | Unique |
| | Parameters | | |
| 14.3.4.2.1 | Summary of Values and Change from | Safety | Repeat |
| | Baseline for Chemistry Parameters | | |
| 14.3.4.2.2 | Shift from Baseline for Chemistry | Safety | Repeat |
| | Parameters | | |
| 14.3.4.3.1 | Summary of Values and Change from | Safety | Repeat |
| | Baseline for Urinalysis Parameters | | |
| 14.3.4.3.2 | Shift from Baseline for Urinalysis | Safety | Repeat |
| | Parameters | | |
| 14.3.5 | Summary of Study Drug | Safety | Unique |
| | Accountability and Compliance | | |
| 14.3.6.1 | Summary of Values and Change from | Safety | Unique |
| | Previous Day for Patient Reported | | |
| | Local Tolerability | | |
| 14.3.6.2 | Shift from Previous Day for Patient | Safety | Unique |
| | Reported Local Tolerability | | |
| 14.3.7 | Summary of Values and Change from | Safety | Repeat |
| | Baseline for Vital Signs | | - |
| 14.3.8.1 | Summary of Prior Medications by ATC | Safety | Unique |
| | Class Level 1 and Preferred Term | | - |
| 14.3.8.2 | Summary of Concomitant Medications | Safety | Repeat |
| | by ATC Class Level 1 and Preferred | | - |
| | Term | | |
| 14.3.8.3 | Summary of Rescue Medications by | Safety | Unique |
| | Class | | |

| 14.3.9.1 | Summary of Values and Change from | Safety | Unique |
|----------|-------------------------------------|--------|--------|
| | Baseline for Rescue Medication Days | | |
| | for All Subjects | | |
| 14.3.9.2 | Summary of Values and Change from | Safety | Unique |
| | Baseline for Rescue Medication Days | | |
| | for Subjects Who Took At Least One | | |
| | Rescue Medication | | |
| 14.3.10 | Summary of Medical History by | Safety | Unique |
| | System Organ Class and Preferred | | |
| | Term | | |

Table 14.3.1 Overall Summary of Treatment Emergent Adverse Events (Safety Population)

| | | B244 O.D. 5.0 | B244 O.D. 20.0 | Pooled B244 | Vehicle |
|--|-----------|---------------|----------------|-------------|-----------|
| | Statistic | (N=xx) | (N=xx) | (N=xx) | (N=xx) |
| Total Number of TEAEs [1] | n | XX | XX | XX | XX |
| Total Number of TESAEs | n | XX | XX | XX | XX |
| Number of Subjects with: | | | | | |
| At Least One TEAE [2] | n (%) | xx (xx.x) | xx (xx.x) | xx (xx.x) | xx (xx.x) |
| At Least One Treatment-Related TEAE [3] | n (%) | xx (xx.x) | xx (xx.x) | xx (xx.x) | xx (xx.x) |
| At Least One Severe (Grade 3) TEAE | n (%) | xx (xx.x) | xx (xx.x) | xx (xx.x) | xx (xx.x) |
| At Least One Treatment-Related Severe (Grade 3) TEAE | n (%) | xx (xx.x) | xx (xx.x) | xx (xx.x) | xx (xx.x) |
| At Least One TEAE Leading to Study Discontinuation | n (%) | xx (xx.x) | xx (xx.x) | xx (xx.x) | xx (xx.x) |
| At Least One TEAE Leading to Death | n (%) | xx (xx.x) | xx (xx.x) | xx (xx.x) | xx (xx.x) |
| At Least One TESAE [4] | n (%) | xx (xx.x) | xx (xx.x) | xx (xx.x) | xx (xx.x) |
| At Least One Treatment-Related TESAE [3] | n (%) | xx (xx.x) | xx (xx.x) | xx (xx.x) | xx (xx.x) |

[1] TEAE: Treatment-Emergent Adverse Event – defined as any AE with onset after the first dose of study medication through 28 days after the last dose of study medication.

[2] Percentage and all subsequent percentages based on the number treated.

[3] Treatment-Related TE(S)AE – defined as TE(S)AE that was considered by the Investigator to be at least possibly related to the study medication.

[4] TESAE: Treatment-Emergent Serious Adverse Event.

Source: Listing XXXX

PROGRAM NAME: XXXXXXXXXX

Table 14.3.1.1 Summary of Treatment Emergent Adverse Events by System Organ Class and Preferred Term (Safety Population)

| | Statistic | B244 O.D. 5.0 (N=xx) | B244 O.D. 20.0 (N=xx) | Pooled B244 (N=xx) | Vehicle (N=xx) |
|---|-----------|-------------------------|--------------------------|-----------------------|-------------------|
| Total Number of TEAEs [1] | n | XX | XX | XX | XX |
| Number of Subjects with at Least One TEAE [2] | n (%) | xx (xx.x) | xx (xx.x) | xx (xx.x) | xx (xx.x) |
| System Organ Class #1 [3,4] | n (%) | xx (xx.x) | xx (xx.x) | xx (xx.x) | xx (xx.x) |
| Preferred Term #1 | n (%) | xx (xx.x) | xx (xx.x) | xx (xx.x) | xx (xx.x) |
| Preferred Term #2 | n (%) | xx (xx.x) | xx (xx.x) | xx (xx.x) | xx (xx.x) |
| Preferred Term #3 | n (%) | xx (xx.x) | xx (xx.x) | xx (xx.x) | xx (xx.x) |
| etc. | | | | | |
| System Organ Class #2 | n (%) | xx (xx.x) | xx (xx.x) | xx (xx.x) | xx (xx.x) |
| Preferred Term #1 | n (%) | xx (xx.x) | xx (xx.x) | xx (xx.x) | xx (xx.x) |
| Preferred Term #2 | n (%) | xx (xx.x) | xx (xx.x) | xx (xx.x) | xx (xx.x) |
| Preferred Term #3 | n (%) | xx (xx.x) | xx (xx.x) | xx (xx.x) | xx (xx.x) |
| etc. | | | | | |

[1] TEAE: Treatment-Emergent Adverse Event – defined as any AE with onset after the first dose of study medication through 28 days after the last dose of study medication.

[2] Percentage and all subsequent percentages based on the number treated.

[3] Subjects will be counted once per System Organ Class/Preferred Term.

[4] MedDRA Dictionary version XX.X was used to code adverse events.

Source: Listing XXXX

PROGRAM NAME: XXXXXXXXXX

DATE: HH:MM/DDMMMYYYY

- Repeat for 14.3.1.6 Summary of Treatment Emergent Adverse Events with \geq 2% Frequency by System Organ Class and Preferred Term for Safety Population
 - Add footnote: TEAEs are presented if they occur in $\geq 2\%$ of subjects in any treatment arm.

| | Severity | Statistic | B244 O.D. 5.0 (N=xx) | B244 O.D. 20.0 (N=xx) | Pooled B244 (N=xx) | Vehicle (N=xx) |
|---|----------|-----------|-------------------------|--------------------------|-----------------------|-------------------|
| Total Number of TEAEs [1] | | n | XX | XX | XX | XX |
| Number of Subjects with at Least One TEAE [2] | | n (%) | xx (xx.x) | xx (xx.x) | xx (xx.x) | xx (xx.x) |
| System Organ Class #1 [3,4] | Mild | n (%) | xx (xx.x) | xx (xx.x) | xx (xx.x) | xx (xx.x) |
| | Moderate | n (%) | xx (xx.x) | xx (xx.x) | xx (xx.x) | xx (xx.x) |
| | Severe | n (%) | xx (xx.x) | xx (xx.x) | xx (xx.x) | xx (xx.x) |
| | Total | n (%) | xx (xx.x) | xx (xx.x) | xx (xx.x) | xx (xx.x) |
| Preferred Term #1 | Mild | n (%) | xx (xx.x) | xx (xx.x) | xx (xx.x) | xx (xx.x) |
| | Moderate | n (%) | xx (xx.x) | xx (xx.x) | xx (xx.x) | xx (xx.x) |
| | Severe | n (%) | xx (xx.x) | xx (xx.x) | xx (xx.x) | xx (xx.x) |
| | Total | n (%) | xx (xx.x) | xx (xx.x) | xx (xx.x) | xx (xx.x) |
| Preferred Term #2 | Mild | n (%) | xx (xx.x) | xx (xx.x) | xx (xx.x) | xx (xx.x) |
| | Moderate | n (%) | xx (xx.x) | xx (xx.x) | xx (xx.x) | xx (xx.x) |
| | Severe | n (%) | xx (xx.x) | xx (xx.x) | xx (xx.x) | xx (xx.x) |
| | Total | n (%) | xx (xx.x) | xx (xx.x) | xx (xx.x) | xx (xx.x) |
| Preferred Term #3 | Mild | n (%) | xx (xx.x) | xx (xx.x) | xx (xx.x) | xx (xx.x) |
| | Moderate | n (%) | xx (xx.x) | xx (xx.x) | xx (xx.x) | xx (xx.x) |
| | Severe | n (%) | xx (xx.x) | xx (xx.x) | xx (xx.x) | xx (xx.x) |
| | Total | n (%) | xx (xx.x) | xx (xx.x) | xx (xx.x) | xx (xx.x) |

Table 14.3.1.2 Summary of Treatment Emergent Adverse Events by System Organ Class and Preferred Term and Severity (Safety Population)

etc.

[1] TEAE: Treatment-Emergent Adverse Event – defined as any AE with onset after the first dose of study medication through 28 days after the last dose of study medication.

[2] Percentage and all subsequent percentages based on the number treated.[3] Subjects will be counted once per System Organ Class/Preferred Term at the highest level of severity.

[4] MedDRA Dictionary version XX.X was used to code adverse events.

Source: Listing XXXX

PROGRAM NAME: XXXXXXXXXX

| | Deletionship | Statistic | B244 O.D. 5.0 | B244 O.D. 20.0 | Pooled B244 | Vehicle |
|---|----------------|-----------|---------------|----------------|-------------|-----------|
| Total Number of TEAEs [1] | Relationship | Statistic | (IN=XX) | (IN=XX) | (IN=XX) | (IN=XX) |
| Total Number of TEAES [1] | | n | XX | XX | XX | XX |
| Number of Subjects with at Least One TEAE [2] | | n (%) | xx (xx.x) | xx (xx.x) | xx (xx.x) | xx (xx.x) |
| System Organ Class #1 [3,4,5] | Definitely Not | n (%) | xx (xx.x) | xx (xx.x) | xx (xx.x) | xx (xx.x) |
| | Unlikely | n (%) | xx (xx.x) | xx (xx.x) | xx (xx.x) | xx (xx.x) |
| | Possibly | n (%) | xx (xx.x) | xx (xx.x) | xx (xx.x) | xx (xx.x) |
| | Probably | n (%) | xx (xx.x) | xx (xx.x) | xx (xx.x) | xx (xx.x) |
| | Definitely | n (%) | xx (xx.x) | xx (xx.x) | xx (xx.x) | xx (xx.x) |
| | Total | n (%) | xx (xx.x) | xx (xx.x) | xx (xx.x) | xx (xx.x) |
| Preferred Term #1 | Definitely Not | n (%) | xx (xx.x) | xx (xx.x) | xx (xx.x) | xx (xx.x) |
| | Unlikely | n (%) | xx (xx.x) | xx (xx.x) | xx (xx.x) | xx (xx.x) |
| | Possibly | n (%) | xx (xx.x) | xx (xx.x) | xx (xx.x) | xx (xx.x) |
| | Probably | n (%) | xx (xx.x) | xx (xx.x) | xx (xx.x) | xx (xx.x) |
| | Definitely | n (%) | xx (xx.x) | xx (xx.x) | xx (xx.x) | xx (xx.x) |
| | Total | n (%) | xx (xx.x) | xx (xx.x) | xx (xx.x) | xx (xx.x) |
| Preferred Term #2 | Definitely Not | n (%) | xx (xx.x) | xx (xx.x) | xx (xx.x) | xx (xx.x) |
| | Unlikely | n (%) | xx (xx.x) | xx (xx.x) | xx (xx.x) | xx (xx.x) |
| | Possibly | n (%) | xx (xx.x) | xx (xx.x) | xx (xx.x) | xx (xx.x) |
| | Probably | n (%) | xx (xx.x) | xx (xx.x) | xx (xx.x) | xx (xx.x) |
| | Definitely | n (%) | xx (xx.x) | xx (xx.x) | xx (xx.x) | xx (xx.x) |
| | Total | n (%) | xx (xx.x) | xx (xx.x) | xx (xx.x) | xx (xx.x) |
| Preferred Term #3 | Definitely Not | n (%) | xx (xx.x) | xx (xx.x) | xx (xx.x) | xx (xx.x) |
| | Unlikely | n (%) | xx (xx.x) | xx (xx.x) | xx (xx.x) | xx (xx.x) |
| | Possibly | n (%) | xx (xx.x) | xx (xx.x) | xx (xx.x) | xx (xx.x) |
| | Probably | n (%) | xx (xx.x) | xx (xx.x) | xx (xx.x) | xx (xx.x) |
| | Definitely | n (%) | xx (xx.x) | xx (xx.x) | xx (xx.x) | xx (xx.x) |
| | Total | n (%) | xx (xx.x) | xx (xx.x) | xx (xx.x) | xx (xx.x) |

Table 14.3.1.3 Summary of Treatment Emergent Adverse Events by System Organ Class and Preferred Term and Relationship to Study Drug (Safety Population)

etc.

[1] TEAE: Treatment-Emergent Adverse Event – defined as any AE with onset after the first dose of study medication through 28 days after the last dose of study medication.

[2] Percentage and all subsequent percentages based on the number treated.

[3] Treatment-Related TEAE – defined as TEAE that was considered by the Investigator to be at least possibly related to the study medication.

[4] Subjects will be counted once per System Organ Class/Preferred Term at the highest level of relatedness.

[5] MedDRA Dictionary version XX.X was used to code adverse events.

Source: Listing XXXX

PROGRAM NAME: XXXXXXXXX

- Repeat for 14.3.1.4 Summary of Severe (Grade 3) Treatment Emergent Adverse Events by System Organ Class and Preferred Term and Relationship to Study Drug for Safety Population
- Repeat for 14.3.2.2 Summary of Treatment Emergent Serious Adverse Events by System Organ Class and Preferred Term and Relationship to Study Drug for Safety Population

Table 14.3.1.5 Summary of Treatment Emergent Adverse Events Leading to Discontinuation from Study by System Organ Class and Preferred Term (Safety Population)

| | Statistic | B244 O.D. 5.0 (N=xx) | B244 O.D. 20.0 (N=xx) | Pooled B244 (N=xx) | Vehicle (N=xx) |
|---|-----------|-------------------------|--------------------------|-----------------------|-------------------|
| Total Number of TEAEs [1] | n | XX | XX | XX | XX |
| Number of Subjects with at Least One TEAE [2] | n (%) | xx (xx.x) | xx (xx.x) | xx (xx.x) | xx (xx.x) |
| System Organ Class #1 [3,4] | n (%) | xx (xx.x) | xx (xx.x) | xx (xx.x) | xx (xx.x) |
| Preferred Term #1 | n (%) | xx (xx.x) | xx (xx.x) | xx (xx.x) | xx (xx.x) |
| Preferred Term #2 | n (%) | xx (xx.x) | xx (xx.x) | xx (xx.x) | xx (xx.x) |
| Preferred Term #3 | n (%) | xx (xx.x) | xx (xx.x) | xx (xx.x) | xx (xx.x) |
| etc. | | | | | |
| System Organ Class #2 | n (%) | xx (xx.x) | xx (xx.x) | xx (xx.x) | xx (xx.x) |
| Preferred Term #1 | n (%) | xx (xx.x) | xx (xx.x) | xx (xx.x) | xx (xx.x) |
| Preferred Term #2 | n (%) | xx (xx.x) | xx (xx.x) | xx (xx.x) | xx (xx.x) |
| Preferred Term #3 | n (%) | xx (xx.x) | xx (xx.x) | xx (xx.x) | xx (xx.x) |
| etc. | | | | | |

[1] TEAE: Treatment-Emergent Adverse Event – defined as any AE with onset after the first dose of study medication through 28 days after the last dose of study medication.

[2] Percentage and all subsequent percentages based on the number treated.
[3] Subjects will be counted once per System Organ Class/Preferred Term.
[4] MedDRA Dictionary version XX.X was used to code adverse events.

Source: Listing XXXX

PROGRAM NAME: XXXXXXXXXX

Table 14.3.2.1 Summary of Treatment Emergent Serious Adverse Events by System Organ Class and Preferred Term (Safety Population)

| | Statistic | B244 O.D. 5.0 (N=xx) | B244 O.D. 20.0 (N=xx) | Pooled B244 (N=xx) | Vehicle (N=xx) |
|--|-----------|-------------------------|--------------------------|-----------------------|-------------------|
| Total Number of TESAEs [1] | n | XX | XX | XX | XX |
| Number of Subjects with at Least One TESAE [2] | n (%) | xx (xx.x) | xx (xx.x) | xx (xx.x) | xx (xx.x) |
| System Organ Class #1 [3,4] | n (%) | xx (xx.x) | xx (xx.x) | xx (xx.x) | xx (xx.x) |
| Preferred Term #1 | n (%) | xx (xx.x) | xx (xx.x) | xx (xx.x) | xx (xx.x) |
| Preferred Term #2 | n (%) | xx (xx.x) | xx (xx.x) | xx (xx.x) | xx (xx.x) |
| Preferred Term #3 | n (%) | xx (xx.x) | xx (xx.x) | xx (xx.x) | xx (xx.x) |
| etc. | | | | | |
| System Organ Class #2 | n (%) | xx (xx.x) | xx (xx.x) | xx (xx.x) | xx (xx.x) |
| Preferred Term #1 | n (%) | xx (xx.x) | xx (xx.x) | xx (xx.x) | xx (xx.x) |
| Preferred Term #2 | n (%) | xx (xx.x) | xx (xx.x) | xx (xx.x) | xx (xx.x) |
| Preferred Term #3 | n (%) | xx (xx.x) | xx (xx.x) | xx (xx.x) | xx (xx.x) |
| etc. | | | | | |

[1] TESAE: Treatment-Emergent Serious Adverse Event.

[2] Percentage and all subsequent percentages based on the number treated.
[3] Subjects will be counted once per System Organ Class/Preferred Term.
[4] MedDRA Dictionary version XX.X was used to code adverse events.

Source: Listing XXXX

PROGRAM NAME: XXXXXXXXXX

Table 14.3.2.3 Summary of Deaths (Safety Population)

| | ~ | B244 O.D. 5.0 | B244 O.D. 20.0 | Pooled B244 | Vehicle |
|---|-----------|---------------|----------------|-------------|-----------|
| | Statistic | (N=xx) | (N=xx) | (N=xx) | (N=xx) |
| Total Number of Deaths | n | XX | XX | XX | XX |
| Related to Disease Under Study [1] | n (%) | xx (xx.x) | xx (xx.x) | xx (xx.x) | xx (xx.x) |
| AE Outcome = Death [2] | n (%) | xx (xx.x) | xx (xx.x) | xx (xx.x) | xx (xx.x) |
| Related to Disease Under Study and AE Outcome = Death | n (%) | xx (xx.x) | xx (xx.x) | xx (xx.x) | xx (xx.x) |

[1] Percentage and all subsequent percentages based on the number treated.
 [2] Corresponds to TEAEs Leading to Death.
 Source: Listing XXXX
 PROGRAM NAME: XXXXXXXXX

| Hematology Parameters | Visit | Statistic | B244 O.D. 5.0 (N=xx) | B244 O.D. 20.0 (N=xx) | Pooled B244 (N=xx) | Vehicle (N=xx) |
|--------------------------------|-----------------------|-----------|-------------------------|--------------------------|-----------------------|-------------------|
| Basophils (10 ⁶ /L) | Screening | n | XX | XX | XX | XX |
| r (· · ·) | 6 | Mean (SD) | xx.x (xx.xx) | xx.x (xx.xx) | xx.x (xx.xx) | xx.x (xx.xx) |
| | | Median | XX.X | XX.X | XX.X | xx.x |
| | | Min, Max | XX, XX | XX, XX | XX, XX | XX, XX |
| | Week 4 | n | XX | XX | XX | XX |
| | | Mean (SD) | xx.x (xx.xx) | xx.x (xx.xx) | xx.x (xx.xx) | xx.x (xx.xx) |
| | | Median | XX.X | XX.X | XX.X | xx.x |
| | | Min, Max | XX, XX | XX, XX | XX, XX | XX, XX |
| | Week 4 CFB [1] | n | XX | XX | XX | XX |
| | | Mean (SD) | xx.x (xx.xx) | xx.x (xx.xx) | xx.x (xx.xx) | xx.x (xx.xx) |
| | | Median | XX.X | XX.X | XX.X | xx.x |
| | | Min, Max | xx, xx | XX, XX | xx, xx | xx, xx |
| | Early Termination | n | XX | XX | XX | XX |
| | | Mean (SD) | xx.x (xx.xx) | xx.x (xx.xx) | XX.X (XX.XX) | xx.x (xx.xx) |
| | | Median | XX.X | XX.X | XX.X | xx.x |
| | | Min, Max | XX, XX | XX, XX | xx, xx | XX, XX |
| | Early Termination CFB | n | XX | XX | XX | XX |
| | | Mean (SD) | XX.X (XX.XX) | XX.X (XX.XX) | XX.X (XX.XX) | XX.X (XX.XX) |
| | | Median | XX.X | XX.X | XX.X | XX.X |
| Repeat for all | | Min, Max | XX, XX | XX, XX | XX, XX | XX, XX |
| Hematology parameters | | | , | | | , |

Table 14.3.4.1.1 Summary of Values and Change from Baseline for Hematology Parameters (Safety Population)

[1] CFB = Change from Baseline. For this analysis, Screening value is used as Baseline. Source: Listing XXXX PROGRAM NAME: XXXXXXXXXX

DATE: HH:MM/DDMMMYYYY

Programming Note:

• Repeat for 14.3.4.2.1 Summary of Values and Change from Baseline for Chemistry Parameters for Safety Population

• Repeat for 14.3.4.3.1 Summary of Values and Change from Baseline for Urinalysis Parameters for Safety Population

| | | | | | Baseline | e Value |
|------------------------------------|-----------------|-------------------|-----------------|-----------|-----------|-----------|
| Hematology Parameters | Treatment Group | Visit | Visit Value [2] | Statistic | Normal | Abnormal |
| Basophils (10 ⁶ /L) [1] | B244 O.D. 5.0 | Week 4 | Normal | n (%) | xx (xx.x) | xx (xx.x) |
| | (N=xx) | | Abnormal | n (%) | xx (xx.x) | xx (xx.x) |
| | | | Normal | n (%) | xx (xx.x) | xx (xx.x) |
| | | Early Termination | Abnormal | n (%) | xx (xx.x) | xx (xx.x) |
| | | | Normal | n (%) | xx (xx.x) | xx (xx.x) |
| | | | Abnormal | n (%) | xx (xx.x) | xx (xx.x) |
| | B244 O.D. 20.0 | Week 4 | | | | |
| | (N=xx) | | Normal | n (%) | xx (xx.x) | xx (xx.x) |
| | | | Abnormal | n (%) | xx (xx.x) | xx (xx.x) |
| | | Early Termination | Normal | n (%) | xx (xx.x) | xx (xx.x) |
| | | | Abnormal | n (%) | xx (xx.x) | xx (xx.x) |
| | | | Normal | n (%) | xx (xx.x) | xx (xx.x) |
| | Pooled B244 | Week 4 | Abnormal | n (%) | xx (xx.x) | xx (xx.x) |
| | | | | | | |

